# Self-Administered Transcranial Direct Current Stimulation for Pain in Older Adults With Knee Osteoarthritis: A Phase II Randomized Sham-Controlled Trial

NCT04016272  
November 7, 2019

Protocol Title:	Self-Administered Transcranial Direct Current Stimulation for Pain in Older Adults with Knee Osteoarthritis: A Phase II Randomized Sham-Controlled Trial
Principal Investigator:	[name]
Co-Investigators:	[name] [name] [name], PhD
Study Coordinator:	[name]
Population:	A maximum of 120 community-dwelling older adults with knee osteoarthritis who are 50–85 years old in Southeast Texas will be enrolled. Participants who meet eligibility criteria will be randomly assigned to either active tDCS (n = 60) or sham tDCS (n = 60).
Number of Sites:	UTHealth School of Nursing is the only site for this study.
Study Duration:	Three years
Subject Duration:	Four months including follow-up assessments

### General Information

- Knee osteoarthritis (OA) is one of the most common pain conditions among people over 45, and the management of OA pain is challenging because the pain is only partially responsive to existing pharmacological approaches, which are often associated with adverse effects. Also, knee OA pain is characterized by increased pain-related brain activation, possibly explaining the limited success of existing peripherally based treatments that target the pain locally in the area of the knee. Therefore, there is growing interest in interventions targeting brain function for this population. One promising treatment is noninvasive transcranial direct current stimulation (tDCS) with the anode over the primary motor cortex (M1) and the cathode over the contralateral supraorbital area (SO) as it can change brain activity in a noninvasive, painless, and safe way. tDCS falls under the category described by the FDA as a “non-significant risk” device. Recent studies suggest that clinic-based M1-SO applied tDCS has promising efficacy for managing chronic pain. However, no investigator to date has examined the effect of the self-administered home-based tDCS on clinical pain. Recent technological advances have increased the portability of tDCS, which creates the potential for home use with real-time monitoring through a secure video conferencing platform of stimulation delivered through electrodes mounted on custom single position headgear to ensure fidelity of treatment localization. The proposed study directly addresses this gap in the literature by investigating the effects of self-administered, remotely supervised M1-SO applied tDCS at home in 120 older adults with knee OA pain using an experimenter- and participant-blinded, randomized, sham-controlled, phase II parallel group (1:1 for two groups) design. The first aim of this study is to

determine the effects of self-administered M1-SO applied tDCS on clinical pain intensity in older adults with symptomatic knee OA. The second aim is to determine the effects of self-administered M1-SO applied tDCS on pain-related cortical response in older adults with symptomatic knee OA. The third aim is to investigate the feasibility and acceptability of self-administered M1-SO applied tDCS in older adults with symptomatic knee OA. This study will provide definite insight into an exciting new modality of nonpharmacological pain self-management in that it will be extremely easy, safe, and noninvasive with minimal side effects.

### **Background Information**

- Arthritis is one of the leading causes of pain, impairments of activities in daily life, and disability in people aged 45 and above. Of the 53 million adults diagnosed with arthritis, more than 22 million (42%) reported trouble with their activities of daily living due to arthritis. Osteoarthritis (OA) is the most common of the arthritic conditions, with the knee being the most commonly affected joint. Patients with chronic pain, such as knee OA pain, do not have sufficient pain relief, and this leads to decreased physical functioning and mobility disability. OA pain is characterized by altered pain and sensory processing in the central nervous system similar to other chronic pain syndromes. Because pharmacologic treatments can increase adverse events among older adults, there is a growing interest in non-pharmacological interventions targeting central nervous system pain processing for this population. Specifically, noninvasive brain stimulation, such as Transcranial Direct Current Stimulation (tDCS), has received significant attention for the treatment of pain in chronic conditions due to its neuromodulatory effect. tDCS involves the application of weak direct electric current to the head in a noninvasive and painless manner, leading to the modulation of the resting membrane potentials of neurons and alteration of the endogenous excitability of the targeted cortical area. This stimulation is believed to mediate analgesic effects by modulating pain processing pathways. Previous studies indicated that tDCS is effective in reducing pain in chronic conditions, including fibromyalgia, spinal cord injury, and multiple sclerosis. Therefore, we will assess the feasibility, acceptability, and efficacy of this novel nonpharmacological treatment option in older adults with knee OA pain. Our hypothesis is that self-administered M1-SO applied tDCS will reduce clinical pain intensity and pain-related cortical response more than sham tDCS

### **Objectives**

- The purpose of this project is to assess the feasibility, acceptability, and efficacy of the self-administered tDCS in older adults with knee OA. The specific aims are the following: (1) To determine the effects of self-administered M1-SO applied tDCS on clinical pain intensity in older adults with symptomatic knee OA, (2) To determine the effects of self-administered M1-SO applied tDCS on pain-related cortical response in older adults with symptomatic knee OA, and (3) To investigate the feasibility and acceptability of self-administered M1-SO applied tDCS in older adults with symptomatic knee OA. Outcome measures include clinical pain intensity, pain-related cortical response using functional near-infrared spectroscopy, and feasibility and acceptability using tDCS experience questionnaire and side effects questionnaire.

## Study Design

- We will conduct a double-blind (participant and experimenter), randomized, sham-controlled, phase II parallel-group study with two groups (sham and active tDCS) in 120 older adults with knee OA.
- Expected duration of study is three years after the IRB approval from CPHS.
- tDCS with a constant current intensity of 2 mA will be applied for 20 minutes per session daily for 2 weeks (Monday to Friday) via the Soterix 1x1 tDCS mini-CT Stimulator device (Soterix Medical Inc., NY; 6.5 inches long, 3 inches wide, 0.7 inches thick) with headgear and 5x7 cm saline-soaked surface sponge electrodes. The FDA has ruled that the aforementioned tDCS stimulator is a “non-significant risk” device, a requirement for Investigational Device Exceptions. The sponge electrodes snap into the custom headgear, which is secured to the participant’s head for simple and fail-safe electrode preparation. This single-position headgear with clearly labeled sponge markers eliminates room for user error and helps conserve the placement of the montage. Participants can only administer a stimulation session via the Soterix 1x1 tDCS mini-CT Stimulator device after being provided a single-use unlock code by the research staff once proper contact quality is achieved (only the on/off button will be adjustable by the study participants; they will not be able to adjust the device settings). After the participant enters the unlock code, the screen on the device will show a timer that counts down the minutes until the end of the session. At 20 minutes, the device will turn off automatically, and study staff will instruct the participant to remove the headset and discard the sponges and to safely store all materials for the next session. For sham stimulation, the electrodes will be placed in the same positions as for active stimulation, but the stimulator will only deliver 2 mA current for 30 seconds. This sham stimulation method has been shown to be reliable and indistinguishable from active treatment.

[figure not shown]

Figure 1. Study flow diagram

## Study Population

- A maximum of 120 community-dwelling older adults with knee osteoarthritis (OA) will be enrolled. Similar to our previous work, participants who are 50-85 years old will be considered eligible if they (1) have symptomatic knee OA based on American College of Rheumatology Clinical criteria, (2) have had knee OA pain in the past 3 months with an average of at least 30 on a 0-100 NRS for pain, (3) can speak and read English, and (4) have no plan to change medication regimens for pain throughout the trial. According to American College of Rheumatology criteria, participants should meet at least 3 of 6 criteria, including age > 50 years, stiffness < 30 minutes, crepitus, bony tenderness, bony enlargement, and no palpable warmth. Participants will be excluded if they have any concurrent medical conditions that could confound the interpretation of outcome measures, pose a safety risk for any of the assessment or tDCS procedures, or preclude the successful completion of the protocol. Specific exclusion criteria are: (1) prosthetic knee replacement or non-arthroscopic surgery to the affected knee, (2) history of brain surgery, brain tumor, seizure, stroke, or intracranial metal implantation, (3) systemic rheumatic disorders, including rheumatoid arthritis, systemic lupus erythematosus, and fibromyalgia, (4) alcohol/substance abuse, (5) current use of sodium channel blockers, calcium channel blockers and NMDS receptor antagonists, (6) diminished cognitive function that would interfere with understanding study procedures (i.e., Mini-Mental Status Exam score ≤ 23), (7) pregnancy or lactation, (8) hospitalization within the preceding year for

psychiatric illness, and (9) no access to a device with internet access that can be used for secure videoconferencing for real-time remote supervision.]

- Participants will be recruited in Southeast Texas under the direction of the PI. We will advertise around local institutions (e.g., UTHealth) and communities by advertisement study flyers. In addition, we will put our recruitment flyer on the UTHealth official social medial channels (e.g., Facebook, Instagram, Twitter, LinkedIn). PI will oversee participant screening and recruitment. Obtaining written informed consent will take place in-person at a scheduled baseline visit.

### Study Procedures

- Participants will do self-administered tDCS at their home or private room for three weeks (Mondays-Fridays) under real-time supervision by the research staff. Data will be collected by study staff across several points using equipment and resources available at [name] (PI's) laboratory at UTHealth School of Nursing (see Table below). Participants will visit UTHealth School of Nursing four times, and each visit will take approximately 2 hours.

Stimulation Session	B	Week 1					Week 2					Week 3					M1	M2	M3	
		1	2	3	4	5	6	7	8	9	10	11	12	13	14	15				
Pregnancy Test	X																			
MMSE	X																			
Knee Radiograph*	X																			
Medical History Questionnaire	X																			
Clinical Pain Intensity																				
NRS (primary outcome)	X	X	X	X	X	X	X	X	X	X	X	X	X	X	X	X	X	X	X	
WOMAC (secondary outcome)	X					X					X						X	X	X	X
PCS (secondary outcome)	X					X					X						X			
Pain-related Cortical response																				
fNIRS imaging (secondary outcome)	X					X					X						X			
QST measures	X					X					X						X			
Feasibility and Acceptability																				
tDCS experience questionnaire (secondary outcome)																	X			
Side effects questionnaire (secondary outcome)		X	X	X	X	X	X	X	X	X	X	X	X	X	X	X				

Note: B, Baseline; M, Monthly follow-up phone assessment after completion of tDCS treatment; MMSE, Mini-Mental Status Exam; NRS, Numerical Rating Scale; WOMAC, Western Ontario and McMaster Universities Osteoarthritis Index; PCS, Pain Catastrophizing Scale; QST, Quantitative Sensory Testing; fNIRS, functional near-infrared spectroscopy. The baseline visit will occur 3 to 7 days prior to the tDCS intervention, and will include medical history questionnaire, clinical pain intensity, and fNIRS imaging. Each month for three months post-intervention, participants will complete a follow-up telephone

assessments of clinical pain intensity. \* Knee radiographs can be scheduled at a different time depending on the participants' availability.

- Pregnancy Test. If participants are a woman of childbearing potential, there may be unknown risks to the fetus. Therefore, pregnancy test by a sample of urine will be obtained in all woman of childbearing potential once at baseline visit.
- MMSE. MMSE will be used to exclude people with diminished cognitive function (i.e., Mini-Mental Status Exam score  $\leq 23$ ).
- Knee Radiograph. Knee radiographs will be taken to determine OA severity using Kellgren-Lawrence scores.
- Medical History Questionnaire. All participants will complete a thorough questionnaire to collect demographic and medical history details, including age, sex, height, weight, duration of knee OA, current and past treatments for knee OA, comorbid conditions, and current medications.
- Clinical Pain Intensity. Clinical pain intensity will be measured by asking participants to rate their average knee pain over the past 24 hours via NRS from 0 (no pain) to 100 (worst pain imaginable). Following Initiative on Methods, Measurement, and Pain Assessment in Clinical Trials recommendations for clinical trials involving chronic pain, pain intensity changes assessed through an NRS will be our primary outcome measure for data analysis purposes. We also measure clinical pain intensity using Western Ontario and McMaster Universities Osteoarthritis Index (WOMAC), which ranges from 0 to 96, with higher scores indicating worse OA pain-related symptoms. Moreover, we measure pain catastrophizing using Pain Catastrophizing Scale (PCS), which ranges from 0 to 52, with higher score indicating higher pain catastrophizing.
- Pain-related Cortical response. We will measure pain-related cortical response using a continuous-wave, multichannel fNIRS imaging system (LIGHTNIRS, Shimadzu, Kyoto, Japan) with three semiconductor lasers at 780, 805, and 830 nm. This instrument encompasses 8 light sources and 8 detectors connected to comfortable headgear using optical fibers. The illumination and detection optodes will be arranged in a geometrical layout that will cover the prefrontal and somatosensory cortex regions bilaterally, consistent with locations investigated in previous studies. In addition, a few optical channels will be located to the primary auditory cortex as a control region that remains inactive during pain stimulation (i.e., both fNIRS and thermal stimulation devices run silently). Based on our hypothesis, we believe these cortical areas will exhibit significant hemodynamic activity elicited by pain stimulation. Hemodynamic image reconstruction will be aided by the acquisition of spatial coordinates of all fNIRS optodes with respect to subjects' anatomical landmarks (nasion, pre-auricular left and right, vertex and inion) using a 3D Digitizer (Polhemus Patriot, Colchester, VT). Optical recordings will be collected during thermal pain stimulation according to the following protocol. A temperature-controlled pain generator (Medoc TSA-II Neurosensory Analyzer) will be used to produce thermal stimulation through a  $16 \times 16 \text{ mm}^2$  thermode placed onto the forearm. The experimental protocol consists of an initial baseline period of 60 seconds during which no thermal stimulation will be applied (i.e., thermode at room temperature), followed by 20-second stimulation at 45°C and a 30-second resting period. This experimental block will be repeated six times, for a total experimental duration of 390 seconds that includes a 60-second resting period at the end of the stimulation chain. The experimental session will last about 20-25 min, including the brain imager setup time. In addition, a multimodal Quantitative Sensory Testing (QST) battery will be completed: heat pain (e.g. threshold, tolerance), pressure pain threshold, punctate mechanical pain (e.g. suprathreshold ratings and temporal summation), and Conditioned Pain Modulation (CPM). These measures will be assessed using equipment and methods available at the [name] laboratory, including a Medoc TSA-II Neurosensory Analyzer and Wagner pressure algometer.

- Feasibility. We will calculate the percentage of participants who a) meet the inclusion criteria, b) agree to be randomly assigned, c) complete the full tDCS protocol, and d) attend the follow-up assessment.
- Acceptability. We will collect data on participants' tDCS experience via a questionnaire, at the conclusion of tDCS treatment on a 0 (strongly disagree) to 10 (strongly agree) scale: 1) It was easy to prepare the device and accessories; 2) The device was unnecessarily complex; 3) The device was easy to use; 4) I felt the video conferences with a technical person were helpful; 5) I would imagine that most people would learn to use this device quickly; 6) The device was cumbersome to use; 7) I felt confident using the device; 8) I needed to learn a lot of things before I could get going with this device; 9) The effectiveness of the treatment increased over the course of treatment; 10) Overall, I felt that transcranial electrical stimulation treatment benefited me. Participants will also be encouraged to elaborate their answers in free-form.
- Moreover, we will evaluate the presence and severity of possible side effects of treatment at the end of each session on a 0 (not at all) to 10 (highest degree) scale. The participants will be asked in an open-ended manner whether they experienced any side effects, and they will then be asked specifically about tingling, itching sensation, burning sensation, pain at the stimulation site, fatigue, nervousness, headache, difficulty concentrating, mood change, and changes in vision or visual perception. If any side effects are reported, the degree of relatedness to the intervention will be assessed on a 5-point scale (details of the data and safety monitoring plan are provided in the Human Subjects section). This approach has been used in our previous study and frequently in other studies.

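### The 24-hour-recall NRS at session 1 is in effect a second baseline: ask it before stimulation, average it with the baseline visit, and do not count it as post-baseline

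*Combined protocol and SAP*

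**What the plan says.** The Clinical Pain Intensity item of Study Procedures asks participants to "rate their average knee pain over the past 24 hours via NRS", on a 0-100 scale, and adds that "pain intensity changes assessed through an NRS will be our primary outcome measure for data analysis purposes". It names no time point, no summary of the repeated ratings and no definition of baseline. The Statistics section does not supply them either.

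The schedule table marks the NRS at baseline, at each of 15 stimulation sessions, and at M1, M2 and M3. The note to the table says: "The baseline visit will occur 3 to 7 days prior to the tDCS intervention". It explains the last three columns as "M, Monthly follow-up phone assessment after completion of tDCS treatment".

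The documents do not say whether the NRS is asked before or after the current is given. Only the side-effects rating has a stated place within the session, which is when the session finishes.

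The treatment period is given as "for three weeks (Mondays-Fridays) under real-time supervision by the research staff" in Study Procedures, but Study Design has "20 minutes per session daily for 2 weeks (Monday to Friday".

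**The concern.** A rating with a 24-hour look-back, taken at the time of a session, describes the day before that session. Two things follow.

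- **Session 1.** Its rating is almost wholly pre-treatment, yet the table places it under the treatment sessions. Because the plan does not define baseline, an analyst could count it as the first on-treatment value. An analyst could equally leave it unused, when it would make the baseline more precise at no cost.
- **Last session.** Its rating carries the effect of all sessions but the last. If it were reported as the result of the full course, the label would be slightly wrong. The table shows no NRS in the days after the last session that could serve instead.

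At stake are the precision of the primary comparison and the meaning of any end-of-course value.

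**Working it through.** **1. The plan's own figures.** The plan gives no figure for the timing of the NRS. Its power statement reproduces: 60 × 0.9 = 54 per arm, and with two-sided alpha of 0.05 (sidedness is my assumption) the minimum detectable effect is (1.960 + 0.842) × √(2/54) = 0.539, or 0.544 with the t distribution, against the stated 0.54. Power at 0.89 is 99.6%, against the stated figure of more than 99%. The point below does not depend on these figures.

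**2. Recall window at session 1.** The window is 24 × 60 = 1,440 minutes and a session lasts 20 minutes.
- Asked just before stimulation: 0/1,440 = 0% of the window is under or after current.
- Asked just after: 20/1,440 = 1.4%, so 98.6% is pre-treatment.

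Only a rating made hours later the same day would change this (12 hours later, 12/24 = 50%). Nothing in the documents suggests that.

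**3. Recall window at the last session.** The same shares apply, so a rating at session k reflects k − 1 completed sessions. That is 14 of 15 on the three-week schedule and 9 of 10 on the two-week text.

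**4. Ratings after the last session.** The NRS row has 19 marks, and 1 (baseline) + 15 (sessions) + 3 (M1-M3) = 19. None is left for a day between the last session and M1. In the copy reviewed, several other rows look shifted by one column. The last fNIRS and QST marks fall under M1, which is a telephone call, although both need laboratory equipment. The four laboratory visits fit baseline plus sessions 5, 10 and 15, so those marks probably belong to session 15. The NRS count is therefore good evidence, but not proof.

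**5. Gain from a two-rating baseline.** Assume a common variance σ² and the same correlation r between any two ratings. The documents give no r.
- Change score, one baseline: 2σ²(1 − r).
- Change score, mean of two baselines: σ²[1 + (1 + r)/2 − 2r] = 1.5σ²(1 − r).
- Ratio: 1.5/2 = 0.75, a **25% reduction** for any r below 1. The standard error falls by 1 − √0.75 = 13.4%.
- ANCOVA, one baseline: σ²(1 − r²). Mean of two: σ²[1 − 2r²/(1 + r)]. Ratio: (1 + 2r)/(1 + r)².

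| r (assumed) | Ratio | Reduction in residual variance |
|---|---|---|
| 0.5 | 2.0/2.25 = 0.889 | 11.1% |
| 0.6 | 2.2/2.56 = 0.859 | 14.1% |
| 0.7 | 2.4/2.89 = 0.830 | 17.0% |
| 0.8 | 2.6/3.24 = 0.802 | 19.8% |

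**6. Sensitivity to equal correlations.** The two baseline ratings are only days apart and may correlate more strongly with each other than with a later rating. Take 0.8 between the baselines and 0.6 with the outcome (both assumed). The change-score variance goes from 2(1 − 0.6) = 0.80 to 1 + 0.9 − 1.2 = 0.70, a 12.5% reduction. ANCOVA residual variance goes from 1 − 0.36 = 0.64 to 1 − 0.36 × 2/1.8 = 0.60, a 6.25% reduction. The gain shrinks but remains.

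**The case against.** The strongest reply is that nothing in the plan misuses the session-1 rating. Listing a rating under a session number does not make it an on-treatment value. The deeper gap, that no primary time point or model is named, is a separate matter. That is fair. What remains is that the plan does not prevent the misuse and leaves a precision gain untaken.

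A reader might infer four stronger things, which the documents do not support.

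- **That pain is never measured after the full course.** M1, M2 and M3 all follow it. What appears to be missing is a rating shortly after the last session. Even that rests on a table with displaced columns: an end-of-treatment visit on a separate day that also took an NRS would close the gap.
- **That the treatment effect is diluted by 1/15 (or 1/10 with ten sessions).** This holds only if all session ratings are averaged, which the plan does not state. If they were, and every other session carried the full effect, 0.89 would become 0.89 × 14/15 = 0.83 with power of 99.0% (0.80 and 98.5% with ten sessions). Only at the minimum detectable 0.54 would power drop noticeably, from about 80% to 73.7% (70.6% with ten).
- **That the lag favours active treatment.** Both arms have the same schedule, so the lag can cost precision or weaken the contrast but cannot create a false benefit.
- **That Monday ratings, which look back over a Sunday without stimulation, need separate handling.** Both arms share this pattern and no consequence for the analysis follows, so no change is asked for.

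The variance reductions are a missed efficiency, not an error, and they depend on assumed correlations. That also stands.

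**Conclusion.** The point holds as one of measurement timing and baseline definition. The session-1 NRS is at least 98.6% pre-treatment if asked at the session, and the last session's NRS omits that session. As far as the table can be read, the next NRS is the month-1 call.

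Using session 1 as a second baseline lowers the variance of a change score by 25%, or ANCOVA residual variance by 11% to 20%, under equal correlations (0.5 to 0.8 for ANCOVA). The gain is smaller if the two baseline ratings are more alike than the later ones. The change score is the closer match to the plan, which describes its primary outcome as a change in pain intensity but names no model.

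The size of the shortfall from omitting the last session is unknown and may be small. The conclusions hold under either the two-week or the three-week treatment period.

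**What to change.** 1. State in Study Procedures that the NRS is asked at each session before the unlock code is issued. This makes session 1 strictly pre-treatment and keeps the sensations of stimulation from colouring the answer.
2. Define baseline in Statistics as the mean of the baseline-visit and session-1 ratings (the one available if the other is missing), and state that session 1 is not a post-baseline value.
3. State which rating is the end-of-course value. If it is the last session's, say that it reflects all sessions but the last. Optionally, add one single-item remote rating about 24 hours after the last session and use that.

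Items 1 and 2 cost a few sentences and no new data. They leave one fewer rating in the treatment period, and the baseline would combine a clinic-visit rating with one taken at a session. The optional rating costs one extra contact per participant, on a Saturday if the last session is a Friday, so its weekday and possibly its mode would differ from the session ratings.

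Separately, the two-week and three-week treatment periods in Study Design and Study Procedures must be reconciled.

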The SMC will comprise 3 members with expertise in neuromodulation, statistics, and geriatric clinical research: [name], professor of psychiatry and behavioral sciences at Baylor College of Medicine; [name], PhD, associate professor and biostatistician at The University of Texas Health Science Center at Houston Cizik School of Nursing; and [name], Roy M. and Phyllis Gough Huffington Chair in Gerontology and the Nancy P. and Vincent F. Guinee Distinguished Chair in Gerontology at The University of Texas Health Science Center at Houston. The SMC members are independent of the project. These members are appropriately qualified to review the scientific design and conduct of the study, to evaluate safety and risks to participants, to interpret data statistically, and to make recommendations concerning continuation, modification, suspension, or termination of the study.

Annual SMC meetings will begin after the first week of data collection. In addition, should any adverse event occur, the SMC will be informed immediately, and a special session will be scheduled to discuss strategies to deal with the event. The annual meeting will include a synopsis of the protocol and design, discussion of the status of interventions and data collection procedures, a summary of subject contacts, discussion of any adverse events or potential adverse events, status of data entry and verification, and a summary of any descriptive and inferential statistics to date. Details about data quality and completeness and data collection timeliness will be provided to the SMC, including enrollment rates, exclusion rates and reasons, completion of scheduled data collection, reasons for study withdrawal, adequacy of enrollment composition, demographic similarities/differences between the intervention and control groups, protocol deviations and adherence, and compromises in confidentiality. The SMC meetings will be closed sessions without the investigators, during which the SMC will discuss the need for additional procedures to prevent adverse events or ensure data integrity. In the unlikely case that the study needs to be terminated early owing to unexpected adverse events or inadequate conduct of the study, the SMC will make recommendations to the investigators.

Recommendations from the SMC meetings will be shared with the UTHealth IRB and the NIH during annual reports and immediately if the SMC identifies adverse events not previously reported or recommends early termination of the study.

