### **Statistics**

- In this study, we will randomly assign 120 individuals to two groups, i.e., 60 participants to each group. With this sample size, we will be able to detect the expected effect size of 0.89 with more than 99% power at a significance level of 0.05 after accounting for 10% attrition. The minimum effect size we can detect with this sample size is 0.54 with 80% power at a significance level of 0.05 after accounting for 10% attrition. Thus, our sample size will provide sufficient power to detect a clinically meaningful effect.
- All data will be analyzed using the intention-to-treat approach. All demographic and clinical variables will be summarized using descriptive statistics, such as mean  $\pm$  standard deviation (SD) or median (interquartile range, IQR) as appropriate for continuous variables and frequency and percentage for categorical variables. The distribution of all variables will be examined to check the validity of distribution assumptions before any analysis, using measures of central tendency and a visual inspection of histograms and quantile-quantile plots. If the normality assumption is not met, equivalent non-parametric approaches will be employed. SAS 9.4 (SAS Institute, Cary, NC) will be used to perform the proposed statistical analyses.

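### The device-experience questionnaire has one end-of-course time point and no provision for early stoppers, so the usability and perceived-benefit part of acceptability may over-represent completers

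*Combined protocol and SAP*

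**What the plan says.** The third aim, under Objectives, is "To investigate the feasibility and acceptability of self-administered M1-SO applied tDCS in older adults with symptomatic knee OA". The same section lists the outcome measures for it as "feasibility and acceptability using tDCS experience questionnaire and side effects questionnaire".

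Under Study Procedures, three sets of measures serve this aim:

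- **Experience questionnaire.** Ten items scored 0-10, on preparation, complexity, ease of use, video support, learning, cumbersomeness, confidence and benefit, plus free text. It records "tDCS experience via a questionnaire, at the conclusion of tDCS treatment". In the schedule table, the row beginning "tDCS experience questionnaire (secondary outcome" has one mark.
- **Side effects questionnaire.** It covers "side effects of treatment at the end of each session on a 0 (not at all) to 10 (highest degree) scale", with an open-ended question, and is marked at all 15 sessions.
- **Feasibility percentages.** Among others, those who "complete the full tDCS protocol, and d) attend the follow-up assessment".

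Elsewhere, the Safety Monitoring Committee receives "reasons for study withdrawal" (A. Monitoring Entity). Section C allows withdrawal at any time and, for a participant who becomes upset, offers either discontinuation or a break; it names no exit measure. Statistics says "All data will be analyzed using the intention-to-treat approach", allows for 10% attrition in the sample size and gives no missing-data method.

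**The concern.** The stated novelty of the trial is self-administration at home. Whether older adults find the device manageable therefore bears directly on its main practical claim, and the ten-item form is where that is measured.

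The plan expects some participants not to finish: it counts completion as an outcome and allows for attrition. A participant who gives up because the headgear or video set-up was too hard holds some of the most useful answers to those ten items, yet nothing in the plan asks for them. If stoppers would have rated the device worse than completers, the reported usability and benefit scores will look better than the experience of everyone who started. Ratings not taken when someone stops may be impossible to recover later.

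**Working it through.** **1. Where the single mark falls.** The table columns are displaced in the extracted text, so I place the mark by logic rather than by header.

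- It shares a column with the last fNIRS, PCS and QST marks.
- fNIRS and QST need laboratory equipment, and the monthly follow-ups are by telephone, so this column is not a monthly call.
- fNIRS has four marks, and Study Procedures states four visits to the School of Nursing. The fourth mark is then the fourth visit.
- WOMAC has a mark in this column and three more after it, which match the three monthly calls.

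The questionnaire is therefore scheduled at the end of the planned course.

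**2. What each Aim 3 measure obtains from someone who stops early.**

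| Measure | From an early stopper | Rates usability or benefit? |
|---|---|---|
| Side effects questionnaire | Yes, for each session attended | No: symptoms such as burning, headache, fatigue |
| Percentage completing | Yes, counted as a non-completer | No: shows stopping, not why |
| Withdrawal reasons to the committee | Yes, on withdrawal from the study | Not named as an Aim 3 outcome |
| Experience questionnaire | No provision stated | Yes, the only one |

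**3. The plan's own figures.** There is none for acceptability. The 10% comes from the sample-size statement, which reproduces: 60 × 0.90 = 54 evaluable per group, and the detectable effect at 80% power, two-sided 0.05, is (1.960 + 0.842) × √(2/54) = 0.539, against the stated 0.54. The 10% is thus an overall attrition allowance in the power calculation, not a forecast of early stopping.

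**4. Illustration of the shift.** Let p be the fraction of responses missing, m the completer mean and s the mean that stoppers would have given.

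- Reported mean = m
- Mean over everyone = (1 − p)m + ps
- Overstatement = p(m − s)

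The documents give none of these three values for the questionnaire. Assume m = 8, and take p from 5% to 20% and s from 6 to 0. The ceiling, 10p, is the case where completers all score 10 and stoppers all score 0.

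| p | Missing of 120 | s = 6 | s = 4 | s = 2 | s = 0 | Ceiling |
|---|---|---|---|---|---|---|
| 5% | 6 | 0.1 | 0.2 | 0.3 | 0.4 | 0.5 |
| 10% | 12 | 0.2 | 0.4 | 0.6 | 0.8 | 1.0 |
| 20% | 24 | 0.4 | 0.8 | 1.2 | 1.6 | 2.0 |

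For example, at p = 10% and s = 4: 0.9 × 8 + 0.1 × 4 = 7.6, against a reported 8.0.

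Items 2, 6 and 8 are negatively worded, so their raw scores shift the other way. With an assumed m = 2 and s = 6 at p = 10%, the reported mean is 2.0 against 0.9 × 2 + 0.1 × 6 = 2.4. Both directions flatter the device.

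**5. When treatment concludes.** Study Design gives 2 weeks, Monday to Friday (2 × 5 = 10 sessions). Study Procedures and its table give three weeks (3 × 5 = 15 sessions). Until these are reconciled, neither the conclusion of treatment nor completion of the full protocol is uniquely defined.

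**The case against.** The strongest reply is that the gap is inferred from silence. A participant's treatment also concludes when that participant stops, the text does not limit the form to completers, and a schedule table shows only the nominal path. Someone who stops stimulation has not necessarily left the study and might still attend the final visit. Section B2 also promises a manual of procedures that may cover early stopping. All of this is possible, but none of it is stated. The only scheduled point is the end of the planned course, staff could reasonably follow it literally, and the manual is not among the documents.

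Two further replies are weaker. The intention-to-treat statement governs how data are analysed and cannot supply answers that were never collected. Withdrawal reasons sent to the monitoring committee are oversight information, not a planned Aim 3 result.

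A reader might infer more than the documents support:

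- **That Aim 3 is answered only by those who finish.** It is not. The side effects form, which Objectives assigns to this aim, covers every session attended, so unpleasant sensations are largely captured. The completion percentage counts every stopper.
- **That the active-sham comparison of experience is biased.** No between-arm test of this questionnaire is specified.
- **That 12 participants will be lost because of the device.** The 10% covers attrition of any kind, including people who finish stimulation and are lost later.

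**Conclusion.** The point holds in a limited form. Followed as scheduled, the plan makes no provision for usability and perceived-benefit ratings from early stoppers, and it has no rule for their missing answers. That part of the acceptability result may over-represent completers; the rest of Aim 3 does include stoppers.

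The size is unknown. The 0.2 to 0.8 points at 10% missing rest on an assumed completer mean of 8, on stoppers rating the device worse, and on treating the whole attrition allowance as missing questionnaires. The shift in a mean would probably be modest, and no acceptability threshold is stated for it to cross. The larger loss is the stoppers' own ratings and comments. For a secondary outcome this does not threaten the trial, but it is worth correcting because the remedy is cheap and missed ratings may not be recoverable.

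**What to change.** 1. **Timing.** In the Acceptability text and the schedule table, give the experience questionnaire at the last stimulation session attended or at discontinuation, whichever comes first. For early stoppers, collect it by telephone or REDCap within a fixed window, for example about a week, and record the reason for stopping.
2. **Reporting.** State respondents over randomised by arm. Give scores for all who started at least one session, then separately for completers and early stoppers, and tabulate reasons for stopping as an Aim 3 result.
3. **Shorter exposure.** Show items 9 and 10 (effectiveness over the course, overall benefit) separately for early stoppers.
4. **Definition.** Reconcile the 2 weeks in Study Design with the three weeks in Study Procedures, so that the conclusion of treatment and completion of the full protocol each have one meaning.

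The cost is one schedule line and a ten-item form with a short call for perhaps a dozen people (12 if the whole 10% allowance were early stopping). The downside is that stoppers rate a shorter exposure, which item 3 addresses.
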